7.4.7. Eliciting and Documenting Adverse Events

The investigator is responsible for ensuring that all AEs and SAEs are recorded in the eCRF and reported to the Sponsor.

Solicited ARs will be collected from Day 1 through 7 days after vaccination. Other (unsolicited) AEs will be collected from Day 1 through 28 days after vaccination.

The MAAEs, AESI, AE leading to withdrawal, AESI, and SAEs will be collected from participants as specified in the SoE ([Table 17](#), [Table 18](#), [Table 19](#), and [Table 20](#)) until the end of their participation in the study. Any AEs occurring before receipt of IP will be analyzed separately from AEs occurring after receipt of the study vaccine.

At every study site visit or telephone contact, participants will be asked a standard question to elicit any medically related changes in their well-being (including COVID-19 symptoms) according to the scripts provided. Participants will also be asked if they have been hospitalized, had any accidents, used any new medications, changed concomitant medication regimens (both prescription and over-the-counter medications), or had any non-study vaccinations.

In addition to participant observations, physical examination findings, or other documents relevant to participant safety classified as an AE will be documented on the AE page of the eCRF.

After the initial AE/SAE report, the investigator is required to proactively follow each participant at subsequent visits/contacts. All AEs and SAEs will be treated as medically appropriate and followed until resolution, stabilization, the event is otherwise explained, or the participant is LTFU (as defined in [Section 6.3](#)).

7.4.8. Assessment of Intensity

An event is defined as “serious” when it meets at least one of the predefined outcomes as described in the definition of an SAE ([Section 7.4.2](#)), NOT when it is rated as severe.

The severity (or intensity) of an AR or AE refers to the extent to which it affects the participant’s daily activities. The Toxicity Grading Scale for Healthy Adult and Adolescent Volunteers Enrolled in Preventive Vaccine Clinical Trials ([DHHS 2007](#)) will be used to categorize local and systemic reactogenicity events (solicited ARs), clinical laboratory test results, and vital sign measurements observed during this study. Specific criteria for local and systemic reactogenicity events are presented in [Section 7.4.3](#).

The determination of severity for all unsolicited AEs should be made by the investigator based upon medical judgment and the definitions of severity as follows:

- Mild: These events do not interfere with the participant’s daily activities.
- Moderate: These events cause some interference with the participant’s daily activities and require limited or no medical intervention.
- Severe: These events prevent the participant’s daily activity and require intensive therapeutic intervention.

Study staff should elicit from the participant the impact of AEs on the participant's activities of daily living to assess severity and document appropriately in the participant's source documentation. Changes in the severity of an AE should be documented in the participant's source documentation to allow an assessment of the duration of the event at each level of intensity to be performed. An AE characterized as intermittent requires documentation of onset and duration of each episode. An AE that fluctuates in severity during the course of the event is reported once in the eCRF at the highest severity observed.

7.4.9. Assessment of Causality

The investigator's assessment of an AE's relationship to IP is part of the documentation process but is not a factor in determining what is or is not reported in the study.

The investigator will assess causality (ie, whether there is a reasonable possibility that the IP caused the event) for all AEs and SAEs. The relationship will be characterized using the following classification:

Not related: There is not a reasonable possibility of a relationship to the IP. Participant did not receive the IP OR temporal sequence of the AE onset relative to administration of the IP is not reasonable OR the AE is more likely explained by another cause than the IP.

Related: There is a reasonable possibility of a relationship to the IP. There is evidence of exposure to the IP. The temporal sequence of the AE onset relative to the administration of the IP is reasonable. The AE is more likely explained by the IP than by another cause.

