7.4. Safety Definitions and Related Procedures

7.4.1. Adverse Event

An AE is defined as any untoward medical occurrence associated with the use of a drug in humans, whether or not considered drug related.

Events Meeting the Adverse Event Definition

- Exacerbation of a chronic or intermittent pre-existing condition including either an increase in frequency and/or intensity of the condition.
- New conditions detected or diagnosed after vaccination even though they may have been present before the start of the study.

Events NOT Meeting the Adverse Event Definition

- Procedures planned before study entry (eg, hospitalization for preplanned surgical procedure).
- Medical or surgical procedure (eg, endoscopy, appendectomy): the condition that leads to the procedure should be the AE.
- Situations in which an untoward medical occurrence did not occur (social and/or convenience admission to a hospital).

An AR is any AE for which there is a reasonable possibility that the vaccine caused the AE ([Section 7.4.3](#)). For the purposes of investigational new drug safety reporting, “reasonable possibility” means that there is evidence to suggest a causal relationship between the vaccine and the AE.

An unsolicited AE is any AE reported by the participant that is not specified as a solicited AR in the protocol or is specified as a solicited AR but starts outside the protocol-defined period for reporting solicited ARs (ie, 7 days after vaccination). Any unsolicited AE which began during mRNA-1273-P301 (COVE) but is ongoing at the time of enrollment in this study, should be documented as medical history.

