7.4.11. Reporting SAEs

Prompt notification by the investigator to the Sponsor of an SAE is essential so that legal obligations and ethical responsibilities toward the safety of participants and the safety of a study intervention under clinical investigation are met.

Any AE considered serious by the investigator or that meets SAE criteria ([Section 7.4.2](#)) must be reported to the Sponsor immediately (within 24 hours of becoming aware of the SAE) via the EDC system. The investigator will assess whether there is a reasonable possibility that the IP caused the SAE. The Sponsor will be responsible for notifying the relevant regulatory authorities of any SAE as outlined in 21 US CFR Parts 312 and 320. The investigator is responsible for notifying the IRB directly.

If the eCRF is unavailable at the time of the SAE, the following contact information is to be used for SAE reporting:

- SAE Mailbox: [contact]
- SAE Fax Line (USA and Canada): [contact]

Regulatory reporting requirements for SAEs are described in [Section 7.4.15](#).

The investigator and any qualified designees are responsible for detecting, documenting, and recording events that meet the definition of an AE, including SAEs, and remain responsible for following up AEs that are serious, considered related to IP or study procedures, or that caused the participant to discontinue the study.

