10.4. APPENDIX 4: Adverse Events of Special Interest Terms

The Investigator's medical judgment must be applied to assess an event as an AESI, as most AESI are based on medical concepts. The table below does not provide a comprehensive list of terms.

The following table describes events/medical concepts that are of interest in COVID-19 vaccine safety surveillance. Some are specific to vaccines; however, some are of interest due to their occurrence in the context of concurrent or recent COVID-19. Events falling into the descriptions below should be reported as AESI, per protocol, even when they occur during/following COVID infection.

Please note: COVID-19 itself is not an AESI.

Medical Concept	Medical Concept Descriptions/Guidance
Anosmia, Ageusia	New onset of anosmia or ageusia associated with COVID-19 or idiopathic etiology. DOES NOT INCLUDE anosmia or ageusia associated with sinus/nasal congestion, congenital, or traumatic etiologies
Subacute thyroiditis	Acute inflammatory disease of the thyroid (immune-mediated or idiopathic). DOES NOT INCLUDE new onset of chronic thyroiditis
Acute pancreatitis	New onset of pancreatitis in the absence of a clear, alternate etiology, such as alcohol, gallstones, trauma, recent invasive procedure, etc.
Appendicitis	Any event of appendicitis
Rhabdomyolysis	New onset of rhabdomyolysis in the absence of a clear, alternate etiology, such as drug/alcohol abuse, excessive exercise, trauma, etc.
Acute respiratory distress syndrome (ARDS)	New onset of ARDS/respiratory failure due to acute inflammatory lung injury. DOES NOT INCLUDE non-specific symptoms of shortness of breath or dyspnea, nor events with underlying etiologies of heart failure or fluid overload
Coagulation disorders	New onset of thrombosis, thromboembolic event, or non-traumatic hemorrhage/bleeding disorder (eg, stroke, DVT, pulmonary embolism, disseminated intravascular coagulation (DIC), etc.)
Acute cardiovascular injury	New onset of clinically confirmed, acute cardiovascular injury, such as myocarditis, pericarditis, arrhythmia confirmed by ECG (eg, atrial fibrillation, atrial flutter, supraventricular tachycardia), stress cardiomyopathy, heart failure, acute coronary syndrome, myocardial infarction, etc. DOES NOT INCLUDE transient sinus tachycardia/bradycardia, non-specific symptoms such as palpitations, racing heart, heart fluttering or pounding, irregular heartbeats, shortness of breath, chest pain/discomfort, etc.

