6.3.1.1. Incidence of Adverse Events

An overall summary of unsolicited TEAEs including the number and percentage of subjects who experience the following will be presented:

- Any unsolicited TEAEs
- Any serious TEAEs
- Any fatal TEAEs
- Any unsolicited medically-attended TEAEs
- Any unsolicited TEAEs leading to discontinuation from participation in the study
- Any unsolicited severe TEAEs
- Any unsolicited AESIs
- Any unsolicited non-serious TEAEs
- Any unsolicited severe non-serious TEAEs

The table will also include number and percentage of subjects with unsolicited TEAEs that are treatment-related per PI's assessment in each of the above categories.

In addition, separate listings containing individual subject adverse event data for unsolicited AEs, unsolicited TEAEs leading to discontinuation from participation in the study, serious AEs and fatal unsolicited AEs will be provided separately.

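### Protocol 7.4.9 states a reasonable-possibility standard for causality but sorts events by whether the vaccine is the likelier cause, which can only lower the treatment-related tables

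*Protocol*

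**What the plan says.** **The standard.** Protocol Section 7.4.9 (Assessment of Causality) sets one question: "The investigator will assess causality (ie, whether there is a reasonable possibility that the IP caused the event) for all AEs and SAEs". Section 7.4.1 and the glossary entry for adverse reaction explain the term. For IND safety reporting, a reasonable possibility "means that there is evidence to suggest a causal relationship between the vaccine and the AE". Section 7.4.11 repeats the standard for serious events: "The investigator will assess whether there is a reasonable possibility that the IP caused the SAE".

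**The categories.** Section 7.4.9 then defines two classes.

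- *Related* asks for a reasonable possibility, exposure and plausible timing, and adds: "The AE is more likely explained by the IP than by another cause".
- *Not related* opens with the absence of a reasonable possibility. It then lists three alternative grounds: no IP received, implausible timing, or "OR the AE is more likely explained by another cause than the IP".

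**The use.** SAP Section 6.3.1.1 counts "unsolicited TEAEs that are treatment-related per PI's assessment in each of the above categories". Section 6.3.1.2 tabulates related unsolicited, serious, severe, medically attended and special-interest events by SOC and PT. Protocol Table 16 lists related unsolicited AEs, related SAEs and related severe AEs.

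**The concern.** The question asked and the answer categories set different thresholds. A reasonable possibility is met by evidence pointing to the vaccine, even when something else is the better explanation. The categories ask for the balance of probability.

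The choice matters more here than in a placebo-controlled trial. The study is open-label, none of its arms is placebo (Protocol Table 11), and no data safety monitoring board is planned (Section 7.5). No concurrent unvaccinated rate is available to set beside the related column.

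A competing cause is also built into some events of interest. Appendix 4 says of its listed AESI concepts that "some are of interest due to their occurrence in the context of concurrent or recent COVID-19", and asks for them to be reported even when they accompany or follow COVID-19. For those events the infection may well be judged the likelier cause, and the stricter test then decides the coding.

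**Working it through.** **1. The two rules compared.** Take an unsolicited event after vaccination, with plausible timing and some evidence for the vaccine. Three cases are possible.

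| Case | Stated standard | Categories of 7.4.9 |
|---|---|---|
| Vaccine likelier than the alternative | Related | *Related* |
| Alternative likelier than the vaccine | Related | *Not related* |
| Equally likely | Related | Neither |

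The second row might be resisted by reading the opening sentence of *Not related* as a condition that must hold as well. The event then falls outside both categories. It still cannot be *Related*, because the last sentence of that definition fails.

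**2. Direction.** Let R be reasonable possibility with exposure and plausible timing, and let L be vaccine likelier than another cause. The stated standard counts R. The categories count R and L together, which is a subset of R. The related count under the categories can therefore equal the count under the stated standard or fall below it. It cannot exceed it.

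**3. Reach.** The SAP takes relatedness from the investigator and describes no second causality assessment for these tables, so any shift passes straight into them. Three things are outside its reach:

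- total counts of AEs, SAEs and AESIs;
- reporting during the study, because 7.4.9 says the judgement does not decide what is reported;
- solicited reactions, which Section 7.4.3 treats as all related.

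**4. Size.** The documents state no figure for related events, so there is nothing to reproduce. If a share s of the events meeting the stated standard has a likelier alternative, 100 such events become 100 × (1 − s). Assumed values of s of 10%, 25% and 50% give 90, 75 and 50. The documents do not say where s lies.

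**5. An illustration that the thresholds differ.** Protocol Section 1.4.2 gives COVE rates for vaccine and placebo. The average share attributable to vaccine is 1 − placebo rate / vaccine rate.

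- Lymphadenopathy-related events, 1.1% against 0.6%: 1 − 0.6/1.1 = 45%. Rounding of the printed rates allows 1 − 0.65/1.05 = 38% to 1 − 0.55/1.15 = 52%.
- Hypersensitivity events, 1.5% against 1.1%: 1 − 1.1/1.5 = 27%. Rounding allows 1 − 1.15/1.45 = 21% to 1 − 1.05/1.55 = 32%.

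Both point to some vaccine effect, yet neither point estimate passes 50%. These are group averages, not judgements on single cases. Section 1.4.2 itself regards the injection site rash and urticaria as likely related, so those cases could pass the stricter test individually. The figures show that the thresholds can part. They do not size the shift.

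**The case against.** The strongest reply is that this is a tension in wording and that nothing shows events were miscoded. Investigators may take the reasonable-possibility sentence at the head of each category as the rule and the rest as guidance. The definition in 7.4.1 is also tied to IND reporting. The first part stands: actual under-counting is not shown. The second part weakens the conflict but does not remove it, because 7.4.9 itself applies the reasonable-possibility question to every AE and SAE.

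Three stronger readings are tempting and are not supported.

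- *A count per arm.* A reader might take the COVE unsolicited AE rate of 23.9%, get 375 × 0.239 = 89.6 participants, assume that 5% to 15% have a likelier alternative, and report 4.5 to 13.4 misclassified. The share is invented. The rate covers the 28 days after each COVE vaccination, not one booster. The placebo rate was 21.6%, so the whole vaccine excess is 375 × 0.023 = 8.6.
- *Serious reactions escaping reporting.* Section 7.4.11 sends every SAE to the sponsor within 24 hours and puts the causality question without any comparison of causes. Section 7.4.5 does the same for the timing of AESIs and requires a narrative. Relatedness does bear on reports of SAEs learned of after participation ends (Sections 5.6 and 7.4.12), but those sections do not invoke the comparative test.
- *A changed safety conclusion.* The primary safety endpoints in SAP Section 3.1 are not conditioned on relatedness. All-cause SAEs and AESIs are tabulated beside the related subsets, the analyses are descriptive, and no decision rule uses the related counts.

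The timing objection also stands. Amendment 11 is dated October 2023 and the last participant was expected to finish in December 2023, so new wording alone would reach few events.

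**Conclusion.** The point holds as an internal contradiction with a known direction and an unknown size. Section 7.4.9 states one threshold and classifies by a stricter one, and it leaves ties without a category. If investigators followed the categories as written, the treatment-related subsets of unsolicited AEs, severe AEs, SAEs, MAAEs and AESIs are equal to or lower than the protocol's stated standard would give. The conclusion on direction rests only on the text. No statement about how many events moved can be made from the documents. A reader of the final report would not know which threshold the related columns reflect, and that is worth settling before the tables are final.

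**What to change.** In Section 7.4.9, delete the comparative clause from each category, so that reasonable possibility, with exposure and plausible timing, sets relatedness. If the sponsor wants the comparative judgement, record a likelier alternative cause as a separate item that does not set relatedness.

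For events already coded, do one of two things before the final CSR:

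- re-assess the unsolicited SAEs and AESIs judged not related because of an alternative cause; or
- state in the CSR which threshold the related tables used, and that ties had no category.

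The information listed in Section 7.4.10 does not name the ground for a *Not related* coding, so a re-assessment may have to work from narratives and source records. Changing the wording without one of these steps would leave two relatedness rules within one report.

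The cost is a protocol edit, a note to sites, somewhat more events reported as related, and a limited review of completed records.

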7.4.10. Reporting Adverse Events

The investigator is responsible for reporting all AEs that are observed or reported during the study, regardless of their relationship to IP or their clinical significance. If there is any doubt as to whether a clinical observation is an AE, the event should be reported.

All unsolicited AEs reported or observed during the study will be recorded on the AE page of the eCRF. Information to be collected includes type of event, time of onset, investigator-specified assessment of severity (impact on activities of daily living) and relationship to IP, time of resolution of the event, seriousness, as well as any required treatment or evaluations, and outcome. The unsolicited AEs resulting from concurrent illnesses, reactions to concurrent illnesses, reactions to concurrent medications, or progression of disease states must also be reported. All AEs will be followed until they are resolved or stable or judged by the investigator to be not clinically significant. The Medical Dictionary for Regulatory Activities (MedDRA) will be used to code all unsolicited AEs.

Any medical condition that is present at the time of screening but does not deteriorate should not be reported as an unsolicited AE. However, if it deteriorates at any time during the study, it should be recorded as an unsolicited AE.

7.4.11. Reporting SAEs

Prompt notification by the investigator to the Sponsor of an SAE is essential so that legal obligations and ethical responsibilities toward the safety of participants and the safety of a study intervention under clinical investigation are met.

Any AE considered serious by the investigator or that meets SAE criteria ([Section 7.4.2](#)) must be reported to the Sponsor immediately (within 24 hours of becoming aware of the SAE) via the EDC system. The investigator will assess whether there is a reasonable possibility that the IP caused the SAE. The Sponsor will be responsible for notifying the relevant regulatory authorities of any SAE as outlined in 21 US CFR Parts 312 and 320. The investigator is responsible for notifying the IRB directly.

If the eCRF is unavailable at the time of the SAE, the following contact information is to be used for SAE reporting:

- SAE Mailbox: [contact]
- SAE Fax Line (USA and Canada): [contact]

Regulatory reporting requirements for SAEs are described in [Section 7.4.15](#).

The investigator and any qualified designees are responsible for detecting, documenting, and recording events that meet the definition of an AE, including SAEs, and remain responsible for following up AEs that are serious, considered related to IP or study procedures, or that caused the participant to discontinue the study.

7.4.12. Time Period and Frequency for Collecting AE, AESI, and SAE Information

Medical occurrences that begin before IP dosing but after obtaining informed consent will be recorded in the Medical History/Current Medical Conditions section of the eCRF and not in the AE section; however, if the condition worsens at any time during the study, it will be recorded and reported as an AE.

AEs may be collected as follows:

- Observing the participant.
- Receiving an unsolicited complaint from the participant.
- Questioning the participant in an unbiased and nonleading manner.

Solicited AEs will be collected from the day of injection through 6 days after vaccination. Other (unsolicited) AEs will be collected from the day of injection through 28 days after vaccination.

Serious AEs (including AESI) will be collected from the start of IP dosing until the last day of study participation.

All SAEs and AESI will be recorded and reported to the Sponsor or designee immediately and under no circumstance should this exceed 24 hours of becoming aware of the event via the EDC system. If a site receives a report of a new SAE or AESI from a study participant or receives updated data on a previously reported SAE or AESI and the eCRF has been taken offline, then the site can report this information on a paper SAE or AESI form using the SAE Mailbox or the SAE Fax line ([Section 7.4.11](#)).

An abnormal value or result from a clinical or laboratory evaluation can also indicate an AE if it is determined by the investigator to be clinically significant (eg, leads to study drug discontinuation, or meets any serious criteria). If this is the case, it must be recorded in the source document and as an AE on the appropriate AE form(s). The evaluation that produced the

value or result should be repeated until that value or result returns to normal or is stabilized and the participant's safety is not at risk.

Investigators are not obligated to actively seek AEs or SAEs after EoS participation. However, if the investigator learns of any SAE (including a death) at any time after a participant has withdrawn from or completed the study, and the investigator considers the event to be reasonably related to the IP or study participation, the investigator must promptly notify the Sponsor.

